#### **3.2. Secondary**

1. Mean automated office SBP at 12 weeks adjusted for baseline values.
2. Other blood pressure measures in active vs. control groups (adjusted for baseline values in each case):
  - a. Mean change (from baseline) in automated office SBP at six weeks.
  - b. Mean automated office SBP at six weeks.
  - c. Mean change (from baseline) in automated office DBP at six and 12 weeks.
  - d. Mean automated office DBP at six and 12 weeks.
  - e. Proportion of patients with hypertension control (percent with SBP < 130 mmHg and DBP < 80 mmHg) at six and 12 weeks.
  - f. Proportion of patients requiring step-up treatment (ever, and at each study time point).
  - g. Proportion of patients with adverse event-free hypertension control (percent with SBP < 130 mmHg and DBP < 80 mmHg).
3. Medical adherence:
  - a. Medication adherence defined by objective pill counts.
4. Health-related quality of life:
  - a. Mean change (from baseline) in health-related quality of life using PROMIS Global Health instrument.

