#### **4. STUDY INTERVENTION**

Patients who are eligible to participate in the trial will be randomized (1:1 allocation) to one of two study arms, and they will take daily:

1. Low Dose Quadruple Therapy (LDQT) comprising candesartan 2 mg, amlodipine 1.25 mg, indapamide 0.625 mg, and bisoprolol 2.5 mg  
OR
2. Candesartan 8 mg

The LDQT includes quarter standard doses of four blood pressure lowering medications, which are currently approved by the US Food and Drug Administration for the treatment of hypertension. The active comparator follows current clinical practice guidelines for the majority of Americans, initiating treatment with an angiotensin II receptor blockers (ARB), which has the best side effect profile of any blood pressure lowering therapy. In both arms, if blood pressure is not controlled (SBP > 130 mmHg or DBP > 80 mmHg) at the six-week follow-up assessment, then study staff will provide participants with an open label pill of amlodipine 5 mg to supplement their study drug, which may be relevant to participants from some race/ethnic groups, including African-Americans. The combination of a calcium channel blocker with an ACE-inhibitor has been demonstrated to be more effective in reducing cardiovascular events than the combination of a thiazide-like diuretic with an ACE-inhibitor based on the ACCOMPLISH trial.

All study drugs, including LDQT, active comparator, and amlodipine add-on will be stored, controlled, and administered centrally. Control of drugs is described in full in the detailed Manual of Procedures. Drug product used in this study is subject to regulatory review and approval through an investigator-initiated investigational new drug (IND) process. Prior to use in human subjects, IND approval will be required.

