2. STUDY OUTCOMES

In the sections below, we include the relevant specific field names for variables within the study database as of the time of SAP creation. These are indicated by the [brackets].

Primary Outcome

Primary efficacy outcome is **mean change (from baseline) in automated office systolic blood pressure (SBP) at 12 weeks** [sbpavg], and analyses will compare this change across arms for primary outcome analyses, adjusting for baseline.

Secondary Outcomes

Secondary efficacy outcomes include:

- 1) Mean automated office SBP at 12 weeks, adjusted for baseline values [sbpavg].
- 2) **Other BP measures** that will be compared across arms, controlling for baseline values:
 - a. Mean change (from baseline) in automated office SBP [sbpavg] at six weeks.
 - b. Mean automated office SBP [sbpavg] at six weeks.
 - c. Mean change (from baseline) in automated office DBP [dbpavg] at six and 12 weeks.
 - d. Mean automated office DBP [dbpavg] at six and 12 weeks.
 - e. Proportion of patients with hypertension control (SBP < 130 mmHg and DBP < 80 mmHg) at six and 12 weeks [sbpavg, dbpavg].
 - f. Proportion of patients requiring step-up treatment [amlo_dispnd].
 - g. Proportion of patients with adverse event-free hypertension control (SBP < 130 mmHg and DBP < 80 mmHg [sbpavg, dbpavg]). For the purposes of this outcome, we will define adverse event-free as absence of any events that are documented as either possibly, probably, or definitely related to study medication ([saerelate] = 3, 4, 5).
- 3) **Medication adherence:** proportion of participants deemed adherent to study medication based on the 80% criterion (i.e., participant took at least 80% of assigned study medication). This information will be captured via:
 - a. Objective pill counts [capsret6, lost6, capsret12, lost12], and
 - b. Self-reported measures [forget, miss30, miss7] in addition to the objective pill counts.
- 4) **Health-related quality of life:** Mean change from baseline in health-related quality of life

using PROMIS Global Health instrument [global01—global10]. There are two domains within this construct:

- a. Global Mental Health (assessed via a T-score)
- b. Global Physical Health (assessed via a T-score)

Safety Outcomes

We plan to evaluate the following safety outcomes:

- 1) Proportion of participants with *any* SAE according to the Good Clinical Practice (GCP) definition [sae_present, saedeath, saelifethrt, saehosp, saedisp, saecong, saeimpevnt].

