Outcome	Variable Type	Model Link Assumption	Note on Covariates
Primary, secondary / exploratory blood pressure measurements at individual study time points	Continuous (assume normality)	Identity	Same as in primary outcome analyses
Dipping at 12 weeks	Binary / categorical	Logit	Indicator of dipping status at baseline in addition to other covariates as in primary analyses
Hypertension control at individual study time points	Binary / categorical	Logit	Same as in primary outcome analyses, including baseline SBP
Requirement for amlodipine add-on therapy	Binary / categorical	Logit	Same as in primary outcome analyses, including baseline SBP
Adverse event-free hypertension control at each study time point	Binary / categorical	Logit	Same as in primary outcome analyses, including baseline SBP
Medication adherence (at least 80%)	Binary / categorical	Logit	Same as in primary outcome analyses, including baseline SBP
Change in PROMIS Global Health	Continuous (assume normality)	Identity	Same as in primary outcome analyses
Indicator for any SAE	Binary / categorical	Logit	Same as in primary outcome analyses, including baseline SBP
Indicator for any relevant side effect	Binary / categorical	Logit	Same as in primary outcome analyses, including baseline SBP
Rate of relevant side effects	Count (Poisson assumption)	Log	Same as in primary outcome analyses, including baseline SBP
Continuous laboratory measurements (potassium, sodium, urea, creatinine)	Continuous (assume normality)	Identity	Same as in primary outcome analyses

Subgroup Analyses and Heterogeneity of Intervention Effects

An exploratory objective of this study is to assess heterogeneity of treatment effect by the following potential hypothesized moderators: age, sex, and race/ethnicity. To address this, we will analyze primary and secondary blood pressure (12-week SBP, DBP) outcomes via the aforementioned

LMMs; we will add an arm-by-<potential moderator> effect in the original model specified above for each potential moderator of interest. Moderation effects will be explored via model-adjusted type III Wald test for fixed effects at the relaxed 10% level of significance. If significant, then we will examine the intervention effect within each subgroup via a series LMMs: male/female, age category, racial/ethnic category.

Agreement between Outcomes

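### The models for hypertension control, event-free control and amlodipine add-on name baseline SBP but not baseline DBP, although each outcome depends on both pressures; the cost is a small loss of precision.

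*SAP*

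**What the plan says.** SAP section 2 lists the outcome as "Proportion of patients with hypertension control (SBP < 130 mmHg and DBP < 80 mmHg) at six and 12 weeks" and the composite as "Proportion of patients with adverse event-free hypertension control (SBP < 130 mmHg and DBP < 80 mmHg", the latter also requiring no event judged at least possibly related to study medication. Add-on amlodipine is given "if blood pressure is not controlled (SBP > 130 mmHg or DBP > 80 mmHg) at the six-week follow-up assessment" (Protocol section 4). Low pressures are therefore needed on both scales for the first two outcomes, and a high value on either scale triggers the third.

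The modeling table in SAP section 6 has a row for "Hypertension control at individual study time points", one for event-free control and one for add-on therapy. All three carry the covariate note "Same as in primary outcome analyses, including baseline SBP". The covariates in SAP section 3 are sex, age, race/ethnicity, literacy score and monotherapy at baseline. Baseline DBP appears in neither place.

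The general text is wider. SAP section 2 places all three outcomes among BP measures "that will be compared across arms, controlling for baseline values". Protocol section 3.2 has the matching line, "Other blood pressure measures in active vs. control groups (adjusted for baseline values in each case". Neither says which baseline values are meant.

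**The concern.** Each outcome is defined on two pressures, but the table adjusts for one. This departs from the plan's usual practice. The basic model in SAP section 6 carries the baseline value of the outcome being modelled, and the dipping row uses "Indicator of dipping status at baseline in addition to other covariates as in primary analyses". For an outcome built from SBP and DBP, the natural counterpart is both baseline pressures.

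DBP is not a minor criterion here. Protocol section 9.1 admits participants on DBP alone, with a lower SBP permitted, so some may fail control on DBP, which baseline SBP predicts only indirectly. SAP section 5 describes no stratification beyond a separate sequence per site, so baseline DBP balance among about 77 analysed participants rests on chance.

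The stakes are precision and clarity for three secondary outcomes. Adjusted odds ratios also depend on the covariate set, so two analysts reading the general promise and the table differently could report different odds ratios from the same data.

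**Working it through.** **1. The plan's own figures.** The documents state no power for these three outcomes. The nearest figure is the initial 80% for a 5 mmHg SBP difference, SD 15, 292 analysed (SAP section 8).

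- Standard error: 15 × √(2/146) = 1.756. Power = Φ(5/1.756 − 1.96) = Φ(0.888) = 81.3%, which agrees.
- ANCOVA, with SD multiplied by √(1 − r²): 90.8% at r = 0.5 and 94.5% at r = 0.6, which agrees with over 90%.
- Current size: 87 × 0.88 = 76.6, about 77.

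**2. Inputs for the check.**

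- From the documents: SBP SD 15; baseline-to-follow-up SBP correlation 0.5–0.6; SBP effect 5 mmHg (SAP section 8) or 6.9 mmHg (the Australian trial, Protocol section 2.3); 77 analysed; 1:1 allocation; two-sided 5%.
- Assumed, not in the documents: DBP SD 10; DBP effect 3 or 5 mmHg; DBP baseline-to-follow-up correlation equal to that for SBP; SBP–DBP correlation 0.3–0.7; control-arm follow-up means 130/80 or 125/82 mmHg.

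**3. What baseline DBP adds.** In this set-up baseline SBP correlates with follow-up DBP at c × r, where c is the SBP–DBP correlation and r the baseline-to-follow-up correlation. With c = 0.5 and r = 0.6, baseline SBP explains (0.3)² = 9% of follow-up DBP variance; baseline DBP explains (0.6)² = 36%.

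A chance difference between arms in mean baseline DBP has standard error 10 × √(1/38 + 1/39) = 2.28 mmHg. The part not accounted for by baseline SBP has standard error 2.28 × √(1 − 0.5²) = 1.97 mmHg. SBP adjustment therefore deals with the imbalance only in part.

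**4. Power.** Correlated baseline and follow-up pressures were simulated, with control = 1 if SBP < 130 and DBP < 80. Two logistic models were fitted to the same simulated trials:

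logit P(control) = α + β·arm + γ₁·SBP₀, with or without + γ₂·DBP₀

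Arm was tested by Wald, as the SAP plans for secondary analyses. There were 4,000 trials per setting. Power in %, n = 77:

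| c | r | Control-arm mean | 5/3 mmHg: SBP only → both | 6.9/5 mmHg: SBP only → both |
|---|---|---|---|---|
| 0.5 | 0.5 | 130/80 | 23.5 → 24.2 (+0.7) | 47.4 → 48.9 (+1.5) |
| 0.5 | 0.5 | 125/82 | 20.9 → 21.4 (+0.5) | 45.8 → 48.9 (+3.1) |
| 0.5 | 0.6 | 130/80 | 24.8 → 26.3 (+1.5) | 48.7 → 51.2 (+2.5) |
| 0.5 | 0.6 | 125/82 | 23.4 → 24.8 (+1.4) | 48.2 → 52.6 (+4.4) |
| 0.3 | 0.6 | 130/80 | 25.1 → 26.8 (+1.7) | 51.8 → 54.8 (+3.0) |
| 0.3 | 0.6 | 125/82 | 23.5 → 25.4 (+1.9) | 49.8 → 54.6 (+4.8) |
| 0.7 | 0.6 | 130/80 | 24.5 → 25.2 (+0.7) | 46.5 → 48.8 (+2.3) |
| 0.7 | 0.6 | 125/82 | 21.6 → 23.2 (+1.6) | 47.5 → 50.9 (+3.4) |

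The Monte Carlo error of each estimate is at most √(0.5 × 0.5/4000) = 0.8 points. The differences are paired, and all 16 are positive. A separate paired set, with and without seven further covariates, gave gains of about 0.5–2.5 points (5/3) and 1.7–3.3 points (6.9/5).

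**5. With the planned covariates.** Sex 1, age 1, race/ethnicity 3, literacy 1 and monotherapy 1 make seven columns, simulated as non-prognostic (6,000 trials per setting). The gain was 0.9 points for 5/3. For 6.9/5 it ran from 1.0 to 5.5, largest where DBP was more often the failing criterion or c was low. Event-free control, mimicked by removing 20% of successes at random, went from 34.8% to 36.5% (6.9/5).

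**6. Type I error.** With no effect, Wald rejection was 4.7% with SBP only and 4.9% with both. With the seven columns it was 5.9% in both models.

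**7. Scale.** Adjusting for SBP alone already gains about 3–9 points over no adjustment. At 292 analysed, the 5/3 effect has 64–73% power with SBP only, against 21–25% at 77.

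**The case against.** The strongest reply is that the plan already covers this. Both documents promise adjustment for baseline values, and a note that the covariates include baseline SBP does not say SBP alone. This part stands: the documents do not show a decision to exclude DBP. But the table is the specific instruction to the analyst, and SBP is the only pressure it names. If DBP was intended, the table is incomplete; if not, the general promise is not fully met.

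A second reply is that the logit model is already crowded. At control rates of 33% and 54%, 39 × 0.33 + 38 × 0.54 = 33 successes are expected. Seven covariates, arm and baseline SBP make 9 slopes, or 3.7 successes per slope; adding DBP makes 10, or 3.3. The caution is fair, but the model is crowded either way, and type I error did not move when DBP was added.

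A third reply is that the DBP inputs are assumed, the model is simpler than the planned mixed model, and event-free control also depends on adverse events. All of this stands, so the size can be given only as a range.

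A reader might infer that the omission wastes power or biases the comparison. The documents do not support either. Treatment is randomised, the outcomes are secondary in a phase II trial, no power is claimed for them, and their low power comes mainly from the sample size.

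**Conclusion.** The point holds as a small gap in the covariate specification. In three rows the table names one of the two baseline pressures on which the outcome turns. The omission costs a little precision and leaves a chance DBP imbalance partly uncorrected, without bias or type I error inflation.

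Under the assumptions listed, adding baseline DBP raises power by about 0.5–2.5 points for a 5/3 mmHg effect and about 1.5–5 points for 6.9/5 mmHg, with single settings at 1.0 and 5.5 once the other covariates are in the model. The direction is consistent; the size is uncertain because no DBP input comes from the documents. The figures are for hypertension control at a single visit. Add-on at week 6 was treated as its complement (readings exactly on a limit aside), and event-free control was checked in one setting only. None of the three outcomes becomes well powered at 77 with either covariate set.

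**What to change.** In the rows for hypertension control, adverse event-free control and amlodipine add-on, change the covariate note to read *including baseline SBP and baseline DBP*. The other rows with the same note (adherence, SAE, side effects) need no change on this ground, as DBP is not part of their definitions.

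If SBP alone is intended, state that and say in SAP section 2 and Protocol section 3.2 which baseline values apply. Either change should be made under SAP version control before database lock.

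The cost is one line of table wording and one more parameter in a logit model with about 77 patients. No new data are needed: baseline DBP is already used for the DBP change outcomes.

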1. INTRODUCTION

This document outlines the proposed analyses for the QUARTET USA phase II clinical trial, which aims to compare clinical and safety outcomes for adult participants with elevated blood pressure (BP) at baseline who receive treatment with ultra-low-dose quadruple-combination therapy (LDQT) to those outcomes in participants given standard dose monotherapy at 12 weeks. Thus, we plan to conduct a two-arm, double-blind randomized controlled trial with equal allocation (1:1) in adults with uncontrolled blood pressure who are eligible for monotherapy. The purpose of this document is to provide detail regarding the statistical analysis plan (SAP) for this study.

Study Aims

The overarching study aims are as follows:

Aim 1: To investigate whether initiating treatment with ultra-low-dose quadruple-combination therapy ("LDQT") including candesartan 2mg, amlodipine 1.25mg, indapamide 0.625mg, and bisoprolol 2.5mg will lower office blood pressure at 12 weeks more effectively, and with no increase in side effects, compared to initiating standard dose monotherapy (candesartan 8mg) in adults with elevated blood pressure who are eligible for monotherapy based on the 2017 AHA/ACC guideline.

We hypothesize that initiating treatment with LDQT will lower office blood pressure at 12 weeks more effectively, and with no increase in side effects, compared to initiating standard dose monotherapy in adults with elevated blood pressure who are eligible for monotherapy.

Aim 2: To investigate whether initiating treatment with LDQT will lower mean 24-hour ambulatory blood pressure at 12 weeks more effectively, and with no increase in side effects, compared to initiating standard dose monotherapy in adults with elevated blood pressure who are eligible for monotherapy.

We hypothesize that initiating treatment with LDQT will lower mean 24-hour ambulatory blood pressure at 12 weeks more effectively, and with no increase in side effects, compared to initiating standard dose monotherapy in adults with elevated blood pressure who are eligible for monotherapy.

Exploratory Aim 1: Assess heterogeneity of treatment effect by hypothesized moderators (age, sex, race/ethnicity, and health literacy level).

We hypothesize that the treatment effect of LDQT will be greater in participants with limited health literacy than those with adequate health literacy. We also hypothesize that treatment effect of LDQT will differ by age, sex, and race/ethnicity subgroups.

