6. STATISTICAL METHODS

Descriptive statistics will summarize participant demographics and baseline clinical outcomes overall and across arms: proportion (percentages) for categorical variables; mean (\pm standard deviation) for continuous variables; and median (interquartile range) for skewed or count variables. Analyses in general will employ normal theory methods and residual diagnostics will evaluate validity of assumptions; where appropriate (i.e., in the event of low cell counts for categorical data or questions of normality), transformation of variables, nonparametric methods, or exact tests may be employed. All primary efficacy and safety analyses will be pre-specified as outlined in this SAP, and deviations from planned analyses or post hoc analyses will be labeled as such in any reports or dissemination materials.

Analyses will assume a two-sided 5% type I error rate unless otherwise specified; there will be some exploratory analyses that will involve a relaxed type I error rate (10%). There will be no corrections made for multiple hypothesis tests, as this is a phase II study evaluating preliminary efficacy.

Planned Primary, Secondary, Safety Analyses

The primary study analysis time point for all relevant outcomes is 12 weeks post randomization. The original analysis plan called for an analysis of covariance (ANCOVA), controlling for baseline value of each relevant outcome in addition to the following baseline covariates: sex, age at baseline, race/ethnicity, health literacy level (indicator of limited literacy as defined by the Newest Vital Sign instrument), and an indicator of monotherapy at baseline (vs. untreated). We deem these variables clinically relevant, important covariates; thus, all analyses will plan for adjustment for these covariates of interest (regardless of statistical significance in the current dataset) in evaluating efficacy of intervention in the present study. However, to better align with the analytic strategies of the QUARTET Australia study, and to make most efficient use of all follow-up data (both six-week and 12-week data), primary analyses will involve a linear mixed model with fixed study arm and baseline outcome value effects and a random participant effect to account for within-participant correlation. We Statistical Analysis Plan: February 9, 2022

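### Subgroup effects are planned only after a 10% interaction test passes, so the differences shown would overstate the true ones; report every subgroup from the interaction model instead

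*SAP*

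**What the plan says.** The subgroup part of SAP section 6 opens: "An exploratory objective of this study is to assess heterogeneity of treatment effect". It names the "potential hypothesized moderators: age, sex, and race/ethnicity" and applies them to "primary and secondary blood pressure (12-week SBP, DBP) outcomes". The test uses the whole sample: "we will add an arm-by-<potential moderator> effect in the original model specified above for each potential moderator of interest". The level is stated: "Moderation effects will be explored via model-adjusted type III Wald test for fixed effects at the relaxed 10% level of significance". The next step is conditional: "If significant, then we will examine the intervention effect within each subgroup via a series LMMs: male/female, age category, racial/ethnic category".

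Neither document plans subgroup estimates when the test fails, or takes them as contrasts from the interaction model. SAP section 3 lists age as one variable, [age], without categories. Race/ethnicity has four categories there, which may be collapsed if counts are low. The mixed model in section 6 uses weeks 6 and 12, and its visit-by-arm and visit terms may be dropped if not significant at 5%. Section 6 also states: "There will be no corrections made for multiple hypothesis tests, as this is a phase II study evaluating preliminary efficacy".

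**The concern.** Under Exploratory Aim 1 the SAP commits itself to an expectation: "We also hypothesize that treatment effect of LDQT will differ by age, sex, and race/ethnicity subgroups". A reader will want to know how large any such difference is. If estimates appear only after a significant test, those that appear are the ones that chance has pushed furthest from zero. With 77 people the test has little power, so this selection is strong.

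Three smaller problems follow from the same paragraph.

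- **Test and estimate come from different models.** On the natural reading of a series of models within subgroups, the test uses one full-sample model and the estimates use separate fits, each re-estimating the baseline slope and five covariates in fewer people.
- **Age changes form.** It is listed as a single variable but followed up by category with no cut stated. A cut chosen late would still look pre-specified, because the SAP already mentions age categories.
- **The time point is unclear.** The target is week 12, but one arm-by-moderator term in a two-visit model, with no visit interaction for the moderator, describes an effect held equal across weeks 6 and 12.

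**Working it through.** **Inputs from the SAP.** Section 8: SD 15 mmHg; baseline to follow-up correlation r of 0.5 to 0.6; 77 analysed of 87 randomized; originally 292 analysed of 365. Section 5: 1:1 allocation. Section 6: 10% level, three moderators, two outcomes.

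**Assumed.** Two subgroups, split 50:50 or 30:70 (the documents give no proportions); a true between-subgroup difference of 5 mmHg or zero; a participant-level ANCOVA in place of the two-visit mixed model.

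**The plan's own figures first.** Per-arm n for 5 mmHg at 80% power is 2 × (1.960 + 0.842)² × 15² / 5² = 141.3, so 142, or 284 in total, close to the stated 292. At 146 per arm, power is 81%. 292 / 0.80 = 365, and 87 × 0.88 = 76.6, about 77. The inputs are consistent. The SAP gives no power or error figure for the subgroup analysis.

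**Standard error of the interaction.** SE = 15 × √(1 − r²) × √(4/n₁ + 4/n₂), with n₁ + n₂ = 77. The estimate passes if it exceeds 1.645 × SE in absolute size. For a true difference of 5, put a = 5/SE. The pass probability is P = Φ(a − 1.645) + Φ(−a − 1.645), and the mean estimate given a pass is 5 + SE × [φ(1.645 − a) − φ(1.645 + a)] / P. With no true difference, the mean absolute estimate given a pass is SE × 2φ(1.645) / 0.10 = 2.06 × SE.

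| r | Split | SE | Must exceed | Pass, true 5 | Mean if passed, true 5 | Mean absolute size if passed, true 0 |
|---|---|---|---|---|---|---|
| 0.6 | 50:50 | 5.47 | 9.0 | 23.8% | 11.7 | 11.3 |
| 0.6 | 30:70 | 5.97 | 9.8 | 21.6% | 12.4 | 12.3 |
| 0.5 | 50:50 | 5.92 | 9.7 | 21.8% | 12.4 | 12.2 |
| 0.5 | 30:70 | 6.46 | 10.6 | 20.0% | 13.1 | 13.3 |

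(SE, thresholds and means in mmHg.) The mean shown is 2.3 to 2.6 times a true 5 mmHg.

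**Sensitivity.** With r = 0 the mean shown is 13.6 to 14.4 mmHg. The SAP's inputs imply a residual SD of 15 × √(1 − r²) = 12.0 to 13.0. With a smaller assumed residual SD of 10.9, a simulation gave a 26% pass rate and a mean of 11.4. At the original 292 analysed and a 50:50 split, the formulas give a 50 to 55% pass rate and a mean of 7.0 to 7.4, so the smaller sample makes the exaggeration worse.

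**Separate fits against the single model** (simulation, r = 0.55, 77 analysed, 6,000 trials per scenario).

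- *Bias.* Without selection, the separate-model difference averages 5.1 for a true 5. The separate fits are therefore not the source of the exaggeration.
- *Precision, with five covariates.* The SE in the smaller subgroup at 30:70 is about 6.2 against 5.5 mmHg. At 50:50 it is 4.45 against 4.26, about 4% larger.
- *Agreement with the test.* Among trials where the interaction test passes, the separate models' own difference has p ≥ 0.10 in 4 to 14% of trials without covariates and 19 to 29% with five. The adjusted figures depend on how covariates are simulated and are approximate.

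**False passes under no heterogeneity.** Three independent tests on one outcome: 1 − 0.9³ = 27%. Six: 1 − 0.9⁶ = 47%. SBP and DBP are correlated, so six tests give at most about 47%.

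**The case against.** The best defence is that the analysis is declared exploratory, in a phase II trial that openly declines multiplicity correction, and that no primary, secondary or safety conclusion depends on it. Testing the interaction before looking within subgroups is also a recognised guard against over-reading each subgroup's own p-value. Both points stand. The first limits the weight of this comment. The second is a reason to keep the test, but not to make estimation depend on it.

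Several stronger readings are tempting, and the documents do not support them.

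- *That the small separate models inflate heterogeneity.* They add noise and can disagree with the test, but they are unbiased. At an even split their cost is slight.
- *That the plan cannot answer Exploratory Aim 1.* The aim is to assess heterogeneity, and the full-sample test does that. Nothing forbids reporting a non-significant interaction estimate; the SAP simply does not plan it.
- *That the 27 to 47% chance of a false pass results from this paragraph's gate.* It results from uncorrected testing at 10%, which the SAP declares and the fix below leaves unchanged.
- *That age is certainly tested as continuous, or that its cut will be chosen from the data.* The first is inferred from a single listed variable. On the second, the SAP does not say when or how the categories are set.

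That the follow-up means separate refits is also a reading, though the natural one.

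**Conclusion.** The concern holds as a minor one. As written, subgroup effects are planned only after a pass at 10%, and with 77 analysed a 5 mmHg difference between two subgroups would be shown about one time in four or five, at about 12 to 13 mmHg on average. A null difference that passes would average about 11 to 13 mmHg in absolute size. For scale, the trial was first sized on an overall effect of 5 mmHg.

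These figures rest on the SAP's SD and correlation, on assumed two-group splits, and on a single-visit approximation. They do not carry over directly to age as a continuous variable or to four race/ethnicity groups, where cells would be smaller and standard errors larger. The direction of the bias does not depend on these choices. The loss of precision, the missing age cut and the unclear time point are secondary and are settled by the same edit.

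**What to change.** Keep the interaction test and replace the conditional sentence in SAP section 6 with text to this effect:

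- For age, sex and race/ethnicity, report the arm effect with 95% CI in every subgroup, and the interaction estimate with its 95% CI, as contrasts from the single full-sample interaction model, whatever the interaction p-value. This replaces the separate within-subgroup models.
- Keep age continuous and show the arm effect at ages fixed in advance, or fix the category cut before unblinding.
- If a week-12 subgroup effect is wanted, keep the visit terms in this model and add visit-by-moderator and visit-by-arm-by-moderator terms. Otherwise state that the contrast averages weeks 6 and 12.

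Without the gate the estimated difference is unbiased (about 5.1 for a true 5 in the simulation). The cost is one SAP paragraph and one extra table, with no new data. The drawback is that wide intervals will be shown for every subgroup, and adding visit-specific terms would add parameters to an already small model.
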